Due to COVID-19, VA ORD has placed an administrative hold on research activities involving non-critical, in-person contacts between study participants and VA research staff. However, VA ORD permits group meetings via platforms that are approved by the ISSO. Following these guidelines, we plan to move the Mobile+Group MBI to an online format which will be delivered weekly, per the study protocol, using University of Minnesota (UMN) Zoom, a VA and HIPAA compliant videoconferencing software. Participants will be required to log into Zoom with a unique code. We will not be video or audio recording the Zoom sessions or collecting PHI or other sensitive participant info. This Zoom technology is on the VA Technical Reference Model (TRM), a list of VA-approved technologies. The UMN Zoom platform is currently being used by Co-Investigators [name] and [name] (NIH #1R21AT009110-01A1), to deliver a Group MBI remotely, due to COVID-19.

The Mobile MBI consists of the same training modules delivered on an app (and available online), with no group interaction but with up to 3 one-on-one phone calls with a facilitator. Inclusion of this condition will allow us to rigorously test the addition of the group component of the MBI. This is important because, although the group experience is considered to be a key part of MBIs and there is some evidence that it increases engagement, there is little research designed to rigorously test the added benefit of groups, relative to its costs. Specifically, the Mobile MBI requires fewer VHA resources (e.g., use of trained facilitators), reduces access barriers associated with scheduling synchronous sessions and reduces barriers associated with the group format. However, the Mobile+Group MBI affords benefits related to having a facilitator and a group (e.g., accountability, support, motivation, feeling of common humanity and shared struggle), which may increase participation, engagement and lead to improved outcomes.

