#### Secondary hypotheses:

- 1. Comparison of intervention groups with secondary outcomes listed below.
- 2. Primary and secondary hypotheses comparisons will be confirmed in gender specific strata.

**Endpoints:** Primary outcome: Change in BPI total score over the 12-month follow-up period. Secondary outcomes will include measures captured in EHR (e.g., medication prescription/refills, health care visits for pain management), as well as patient-reported measures related to pain, comorbid mental health conditions and function, expected mediators of treatment effects, patient satisfaction, and adverse effects. These outcomes will be assessed at 10 weeks, 6 months and 12 months.

**Randomization.** Participants will be randomized to Mobile+Group MBI, Mobile MBI or Usual Care (UC; 1:1:1) after all eligibility components are completed. (See 5.4 for eligibility component details.) During the phone call the participant will be randomized and will be told whether they have been selected to be in UC or one of the two intervention groups. The randomization list will be concealed from the research team within the tracking application, so team members will not know the next study assignment. Permuted blocks will be used to aid in the concealment of treatment assignment while ensuring balance in treatment arms across time.

**Usual Care Control Condition.** Participants assigned to the Usual Care (UC) condition will be told their group assignment during the randomization phone call described in the Randomization paragraph above. They will also be mailed a letter confirming their assignment.

**Intervention Conditions.** Participants assigned to the Mobile MBI or Mobile+Group MBI intervention groups will be told their group assignment during the randomization phone call

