**Mobile+Group MBI.** The Mobile+Group MBI offers the same weekly lessons as described for the Mobile MBI and also includes a group component delivered via UMN Zoom, a VA and HIPAA compliant videoconferencing software (see description on p. 18). Participants in the Mobile+Group MBI will be enrolled in a group with other Veteran study participants with chronic pain, who will gather about weekly (8 sessions, each approximately 1.5 hours long) to view online narrated videos, guided meditations and mindfulness exercises, presented by a trained mindfulness instructor. These online components will be interspersed with group discussions led by a facilitator. These facilitators will not be certified in MBSR but will have sufficient familiarity and understanding of mindfulness and MBIs to provide participant support (see Facilitator Training below). This has several advantages. First, it will facilitate consistency and fidelity across study cohorts. Second, by not needing extensive training and certification of facilitators (which is what is required for MBSR instructor certification), there is a greater likelihood that the intervention can be adopted and sustained in VA settings. From a future implementation perspective, it will allow us to use existing VA staff as facilitators. We have already identified staff members who are interested in facilitating through a preliminary study at the Minneapolis VAHCS. Participants will also have access to the email and telephone support lines that those in the Mobile MBI condition will have access to (described in the section above).

Table 1: Components of Mobile+Group MBI and Mobile MBI, compared to Standard MBSR				
Feature	Standard MBSR	Mobile+Group MBI	Mobile MBI	Purpose of
	Course			modification
Кеу	Intention, attention	Same as MBSR	Same as MBSR	N/A
Components	and attitude			

Table 1: Components of Mobile+Group MBI and Mobile MBI, compared to Standard MBSR				
Feature	Standard MBSR Course	Mobile+Group MBI	Mobile MBI	Purpose of modification
Mindfulness Skill Building	Instruction, exercises in perceptions, stressors, presence, embodiment, habits, stress reactivity, maladaptive coping, and cognitive reappraisal, community building, applicability to everyday life, and establishing accountability and resources; meditation practice	Same as MBSR	Same as MBSR	N/A
Total hours	29-33 hours	12+ hours	9+ hours	

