Class schedule	Introductory session: 2.5 hrs; 8 weekly sessions lasting 2.5 hours each; 6 ½-8-hour retreat	8 weekly sessions, 1.5 hours each (45 min. recorded session, 45 min. group with option to review again, at own pace at home) & 1 technical session	8 weekly sessions, 30-60 minutes each (with option to review again at own pace) & 3 scheduled check-ins	Reduced class schedule to improve adherence/ sustainability
Delivery method/ Instructors	In person, group sessions, delivered by certified MBSR instructors	Group settings, using pre-recorded online lessons presented by a trained mindfulness instructor interspersed with group discussions led by a trained facilitator (not required to be an expert in MBSR)	Online, individual based, using pre- recorded online lessons presented by a trained mindfulness instructor; written reflective exercises (done on own) replace group discussion	MBSR- or mindfulness- trained instructor not required; increases reach; Asynchronous (Mobile MBI)

Feature	Standard MBSR Course	Mobile+Group MBI	Mobile MBI	Purpose of modification
Out-of-class mindfulness practice	≥45 minutes daily	Up to 20 minutes daily guided meditation on the app (with opportunity for additional practice, including very brief guided meditation of 1-5 minutes); guided meditations to do during daily activities (e.g., walking, eating) and in response to pain and co-occurring states that can trigger maladaptive coping responses (e.g., stress, anxiety, anger).		Shorter practice sessions to improve adherence and sustainability; opportunity to use mindfulness to inhibit maladaptive and activate adaptive pain responses
Resources provided	Audio CDs for practice (Guided Mindfulness Meditation, Series 1 and 2) and Course Workbook	Mobile application including video, audio, available online and offline, guided/unguided of varying lengths. Course workbook available in hard and electronic copy.		Mobile+Group MBI participants have opportunity to make up or review missed sessions via the app
Behavioral change strategies		Use of mobile tools to behavioral change stra monitoring, feedback o activation of adaptive related response strate time".	tegies such as self- on performance; pain and stress-	Increase adherence to class sessions and practice; inhibit maladaptive and activate adaptive pain responses

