facilitator/coach): Co-I [name] (who has substantial experience training facilitators to deliver selfcare interventions for pain conditions); PI [name] (who has experience training counselors to deliver a self-management intervention for Veterans with chronic pain), and [name], who was the primary facilitator for the pilot study. The goals of the proposed facilitator training are to empower individuals within the VA system to be able to support MBIs in a sustainable fashion, and to ensure consistency and reliability in MBI delivery (treatment fidelity). We will provide standardized training to ensure facilitators have the necessary skills and comfort levels to deliver the intervention. Given that the facilitators will play a supportive role to the standardized mindfulness based online video recordings, focus will be placed on developing skills that encourage reflection and discussion about patients' experiences with mindfulness (similar to what would occur in an MBSR program). Basic skill building will focus on establishing rapport; remaining on schedule and adapting as necessary; applying principles of the program to patients' situations; encouraging patient involvement; pacing sessions effectively; using effective interpersonal skills; and exercising professionalism and judgement. More advanced skills also will be addressed including effective communication such as using open-ended questions; providing affirming responses; reflecting; providing summaries; and dealing with resistance.  Initial training will include interactive workshops presented via videoconference (total of about 8 hours) scheduled at times convenient for facilitators. These will be supplemented by webinars and online training (total of about 8 hours). Videoconferences (about monthly for 1 hour) will be held and led by [name], [name], and [name], to build a community of practice to problem-solve, facilitate consistency, and ensure adherence to study protocols, between facilitators and across sites. Annual refresher training will include workshops (total of about 4 hours) with webinars and online training modules (total of about 2 hours). Fidelity to group sessions will be assessed through structured fidelity checklists (adapted from those used previously)  applied to random observation of intervention sessions (10%).

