#### General Analytic Approach.

We will use an intention-to-treat approach. Preliminary descriptive analyses will summarize the distributions of the baseline measures across treatment arms overall and by gender and will similarly assess the outcome distributions across assessment time points. We will summarize the completeness of the self-reported outcome assessments and examine associations between completeness and baseline measures as well as the association with secondary outcome assessments that are collected from the electronic medical record (e.g. medications, health care utilization related to pain treatment). In previous studies, we have observed outcome completion rates in excess of 90% at each assessment time-point. Initial analyses will use all

available follow-up data and subsequent sensitivity analyses will examine the potential effect of response bias.

For analyses of the primary outcome, all repeated measurements of the BPI score will be fitted in a mixed model for repeated measures as a function of the group assignment, while controlling for time points and baseline values of the outcome as fixed effects, with participants as random effects. Between-group differences over the entire follow-up period will be tested as the primary test of treatment group differences (this will be done for all three comparisons of the Mobile, Mobile+Group, and Usual Care arms). Between-group differences will be estimated for each of the time points (e.g. 10 weeks, 6 months and 12 months). The secondary outcomes physical function, anxiety, depression, fatigue, sleep disturbance, participation in social roles and activities, patient-ratings of improvement, and PTSD) will be similarly analyzed using the same linear mixed effect models for normal continuous measures and appropriate generalized linear mixed effect models for non-normal measures. For example, the BPI responder analyses will use generalized linear mixed effect models with binomial distributions and either log or logit links, which ever best fit the data, for the repeated dichotomous outcomes of a 30% reduction from baseline in BPI scores over the 12-month study period.

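### The primary model has no term for the Zoom groups that exist only in the Mobile+Group arm, so a shared-group or shared-facilitator effect on BPI would push two of the three primary tests above 0.0167, by an amount that may be slight

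*Combined protocol and SAP*

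**What the plan says.** Section 5.1 (Randomization) allocates individuals: "Participants will be randomized to Mobile+Group MBI, Mobile MBI or Usual Care (UC; 1:1:1".

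Section 5.1 (Mobile+Group MBI) says that participants in that arm "will be enrolled in a group with other Veteran study participants with chronic pain, who will gather about weekly", for 8 sessions of about 1.5 hours with discussion led by a facilitator. Table 1 splits each session as "45 min. recorded session, 45 min. group with option to review again, at own pace at home". Section 2.0 describes the Mobile arm as the same modules "with no group interaction but with up to 3 one-on-one phone calls with a facilitator". No groups are described for Usual Care.

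Section 5.6 (General Analytic Approach) fits all follow-up BPI scores by group assignment, "controlling for time points and baseline values of the outcome as fixed effects, with participants as random effects", and tests all three pairwise contrasts over the whole follow-up. Differences at 10 weeks, 6 months and 12 months are also estimated. The sensitivity analyses described there address response bias. Section 5.6 (Power and Sample Size Estimate) gives 80% power at an effect size of 0.33 with 200 completers per arm and alpha 0.0167 per comparison. It states no design effect.

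**The concern.** A participant random effect handles repeated scores from one person. It does not handle likeness between people who spend eight sessions with the same peers and facilitator. If that shared setting moves their BPI scores together, the Mobile+Group mean is less precise than the model believes. Confidence intervals for the two contrasts that use that mean would be too narrow, and their tests would exceed the Bonferroni level. One of the two is primary hypothesis 3, which tests the added value of the group itself.

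More recruitment does not cure this. At a given group size and ICC, the ratio of true to modelled standard error does not depend on the number of participants.

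**Working it through.** **Inputs from Section 5.6.** Alpha 0.05/3 = 0.0167 per contrast; 200 completers per arm; effect size 0.33. Sidedness is not stated; two-sided is assumed because it fits the stated power.

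**Assumed.** Group size m and ICC, shown over a range.

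**Reproducing the plan.** z = 2.394. Power at 0.33 = Φ(0.33/√(2/200) − 2.394) = Φ(0.906) = 81.8%, against 80% stated (one-sided would give 88.0%). The responder differences in the same section (13.3, 14.3 and 16 points from 15%, 20% and 35%) give 80.2%, 79.8% and 80.2% with independent participants. The power section therefore makes no allowance for groups.

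**Adding groups in one arm.** The variance of the Mobile+Group mean is multiplied by D = 1 + (m − 1)·ICC. For a contrast with an ungrouped arm, r = (1 + D)/2. Then:
- true/modelled SE = √r
- actual alpha = 2·[1 − Φ(2.394/√r)]
- detectable effect at 80% power, once clustering is allowed for = (2.394 + 0.842)·√(2r/200)
- power at 0.33, likewise = Φ(0.33/√(2r/200) − 2.394)

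Example, m = 10 and ICC 0.05: D = 1 + 9 × 0.05 = 1.45; r = 1.225; √r = 1.107; alpha = 2·[1 − Φ(2.163)] = 0.031.

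| ICC (m = 10) | SE ratio | alpha, each Mobile+Group test | familywise error | detectable effect (SD) | power at 0.33 |
|---|---|---|---|---|---|
| 0 | 1.00 | 0.017 | 0.044 | 0.32 | 82% |
| 0.01 | 1.02 | 0.019 | 0.048 | 0.33 | 80% |
| 0.05 | 1.11 | 0.031 | 0.066 | 0.36 | 72% |
| 0.10 | 1.20 | 0.047 | 0.091 | 0.39 | 64% |

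Familywise error comes from numerical integration over three independent arm means with variances in the ratio D : 1 : 1. It passes 0.05 when (m − 1)·ICC exceeds about 0.129, which is an ICC of 0.026 with 6 per group, 0.014 with 10, or 0.009 with 15. At ICC 0.05 the per-test alpha is 0.024 with 6 per group and 0.039 with 15.

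**Simulation** (20,000 trials, m = 10, ICC 0.05): 0.0310 and 0.0306 for the two Mobile+Group tests, 0.0163 for Mobile vs Usual Care, familywise 0.067.

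**Sorting only.** When people were merely sorted into groups by a trait related to outcome, with no effect of the group itself, an observed ICC of 0.10 gave alpha 0.0179. That is within about 1.3 Monte Carlo standard errors of 0.0167.

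**Three visits.** The ICC in the table refers to the baseline-adjusted follow-up mean. Assume baseline correlation rb = 0.3–0.5 and correlation between follow-ups rf = 0.6–0.7. The variance of that mean is V = (1 + 2·rf)/3 − rb² = 0.48–0.71, and a single-visit ICC of 0.05 becomes 0.05·w²/V:
- effect lasts 12 months (w = 1): 0.07–0.10, alpha 0.037–0.048
- halves after week 10 (w = 2/3): 0.03–0.05, alpha 0.025–0.029
- week 10 only (w = 1/3): about 0.01, alpha 0.019–0.020

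**The case against.** **Only some correlation counts.** A reader might infer that any within-group correlation inflates error. It does not, as the sorting check shows. Sorting is possible here because groups meet at set dates and times (Section 5.4). The point is limited to correlation caused by a shared group or facilitator. This objection stands.

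**Section 2.0 is not evidence of clustering.** It is tempting to cite the statement that the Mobile+Group arm "affords benefits related to having a facilitator and a group (e.g., accountability, support, motivation, feeling of common humanity and shared struggle". That describes an average benefit of groups over no groups, not variation between groups. The plan's other features suggest a low ICC: "facilitators will play a supportive role to the standardized mindfulness based online video recordings", and "Fidelity to group sessions will be assessed through structured fidelity checklists". This also stands. The documents neither establish an ICC nor justify assuming zero.

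**The effect may be negligible.** At ICC 0.01 with 10 per group, familywise error stays below 0.05, and an effect confined to week 10 is diluted in the 12-month contrast. True, and it limits the weight of the point.

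**Group size may be stated elsewhere.** Most of Section 4.0 was not available for this review, so nothing can be said about what it contains.

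**A reader might infer that the trial is underpowered.** The documents do not support that for the difference of around 0.5 SD that Section 5.6 calls clinically important. On the same formula, power at 0.5 SD with 200 per arm is about 99% / 98% / 96% at ICC 0.01 / 0.05 / 0.10 with 10 per group.

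**Conclusion.** The gap is real, and its size is unknown. Followed as written, the plan gives standard errors that are too small for two of the three primary contrasts whenever a shared group or facilitator makes BPI outcomes correlate. With 10 per group, the excess runs from slight (0.019 per test at ICC 0.01) to nearly threefold (0.047 at ICC 0.10). Those figures rest on an assumed group size, an assumed ICC on the analysed scale, equal group sizes and two-sided tests. The omission of a group term is certain from Section 5.6; its practical importance is not. This is a cheap improvement, best made before analysis.

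**What to change.** 1. **Primary BPI model and linear secondary models.** Record a Zoom-group ID; Table 2 lists class attendance but no group identifier. Add a random effect for assigned Zoom group in the Mobile+Group arm only, with Satterthwaite or Kenward-Roger degrees of freedom. Keep non-attenders under their assigned group. Keep the model if the group variance is estimated at zero, and use small-sample-corrected cluster-robust standard errors only if it does not converge.

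   In simulation (100,000 trials per ICC, 20 groups of 10, a single outcome), this gave per-test alpha 0.013–0.018 and familywise error 0.037–0.048 over ICC 0–0.10. The variance was estimated at zero in 54% of trials at ICC 0 and 43% at ICC 0.01, so a rule that changes estimator at zero would often be triggered.

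2. **Contrasts at 10 weeks, 6 months and 12 months.** Let the group effect vary by visit, or use cluster-robust standard errors. Suppose the effect exists only at week 10, with ICC 0.05 there and 10 per group. A constant group effect then recovers only (1/3)² of the group variance: modelled r = 1.025 against a true 1.225. The week-10 test read at 0.0167 would still run at 2·[1 − Φ(2.394·√(1.025/1.225))] = about 0.029.

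3. **Facilitators.** If one facilitator leads several groups, add a facilitator-level sensitivity analysis.

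4. **Responder and other non-linear outcomes.** Keep the planned mixed model and add a cluster-robust or GEE sensitivity analysis by Zoom group with a small-sample correction. Note that unweighted GEE estimates a population-averaged effect and needs a stronger missing-data assumption, which matters when Section 5.6 allows for up to 20% without complete follow-up.

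5. **Power section.** Say that 80% power at 0.33 assumes no within-group correlation, or show 0.33 / 0.36 / 0.39 SD for the two Mobile+Group contrasts at ICC 0.01 / 0.05 / 0.10 with 10 per group.

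**Cost.** Analysis-plan wording and one added variable; no extra participants. Intervals for the two Mobile+Group contrasts widen by the SE ratios in the table. In simulation with Satterthwaite degrees of freedom, power at 0.33 falls from 82% to 79% if there is no clustering, and is 77% / 70% / 61% at ICC 0.01 / 0.05 / 0.10. The group term cannot separate sorting from a true group effect, so it is conservative where sorting is the only source.

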#### Power and Sample Size Estimate

Our power calculation uses the total BPI score as the primary outcome measure. For our primary analysis we estimate there will be 200 participants in each of the three treatment arms with complete data for a total of 600 people with complete data from a total of up to 950 randomized. Two hundred participants in each arm would yield 80% power to reject the null hypothesis of equal means if any of the three arms differed from each other by an effect size of 0.33 or greater. This is based on an alpha level of 0.0167 (Bonferroni correction of 0.05/3 = 0.0167) for each of the three comparisons (Mobile+Group vs Usual Care, Mobile vs Usual Care, and Mobile+Group vs Mobile). Using the same assumptions, there would be 90% power to detect differences of 0.38 or greater. The BPI has been found to have a minimally clinically important difference of approximately 1 point and the standard deviation from prior studies is around 2 points, which is consistent with a minimally important clinical difference in effect size of around 0.5.

As a secondary analysis we will look at a categorical responder analysis, in which we define clinically significant changes as a 30% reduction in BPI score from baseline. This is an accepted threshold for clinically significant improvement in clinical trials and recommended by the IMMPACT guidelines.

Previous studies demonstrate that a 30% reduction on the BPI is a clinically important difference. Prior studies have shown that 15-20% of UC patients demonstrate a 30% reduction in pain function score from baseline to follow-up. With 200 people in each arm there would be 80% power to detect absolute differences of greater than 13.3%, 14.3%, and 16%, respectively, based on assumptions of 15%, 20% or 35% in the comparison arms (accounting Bonferroni corrections for comparisons of Mobile+Group vs Usual Care, Mobile vs Usual Care, and Mobile+Group vs Mobile).

Based on the conservative estimate of 20% attrition, we propose randomizing at least 250 per arm to ensure that we maintain a minimum effective size of 200 per group (250 people per group\*.80=200). If we instead achieve the anticipated attrition rate of only 10% then our sample will be approximately 225 per arm.

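### The primary model's only stated within-person term is a participant random effect; read literally it assumes equal variance and correlation at all visits, so visit-specific intervals may be miscalibrated

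*Combined protocol and SAP*

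**What the plan says.** The General Analytic Approach in section 5.6 states that the BPI scores "will be fitted in a mixed model for repeated measures as a function of the group assignment", "controlling for time points and baseline values of the outcome as fixed effects, with participants as random effects". The section gives no residual covariance structure, random slope, robust standard error or fallback structure.

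Two uses of the model follow. The confirmatory one is pooled over visits: "Between-group differences over the entire follow-up period will be tested as the primary test of treatment group differences". The other is by visit: "Between-group differences will be estimated for each of the time points (e.g. 10 weeks, 6 months and 12 months"). The continuous secondary outcomes are to be "similarly analyzed using the same linear mixed effect models for normal continuous measures", so whatever covariance is used for BPI carries over to them.

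The initial analysis uses all available follow-up data. Weighted selection models covering missing-at-random and missing-not-at-random mechanisms are planned as sensitivity analyses. On inputs, the power section gives one BPI standard deviation of about 2 points, an important difference of about 1 point, and a planning allowance of 20% attrition. It gives no visit-specific SDs and no correlations.

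**The concern.** A single participant effect with independent residuals is compound symmetry. In a trial with a baseline covariate this often fits poorly. Baseline usually predicts an early visit better than a late one, so the variance left after adjustment tends to grow. Adjacent visits also tend to correlate more strongly than distant ones. A model that pools the variance then gives every visit roughly the same standard error: too large where the true variance is small, too small where it is large.

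At stake are the intervals at 10 weeks, 6 months and 12 months, and the corresponding intervals for the continuous secondary outcomes. Persistence of effect is a theme of the Introduction, which contrasts a trial whose differences lasted to 52 weeks with one whose effect was gone by 6 months. Readers will therefore look at the 12-month interval. With dropout, a likelihood analysis also relies on the covariance to carry information from observed to missing visits, so a wrong structure can leave some bias.

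**Working it through.** **The plan's own figures.** The documents state nothing numerical about covariance, so the only figures to reproduce are those for sample size. With 200 per arm and two-sided alpha 0.05/3 = 0.0167 (critical value 2.394):
- Effect size 0.33: 0.33 × √(200/2) = 3.30, and power = Φ(3.30 − 2.394) = 81.8%, against 80% stated.
- Effect size 0.38: Φ(3.80 − 2.394) = 92.0%, against 90% stated.
- Attrition: 200/0.80 = 250 per arm.

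The stated figures are reproduced, slightly on the safe side. This calculation is a two-sample comparison with no covariance input, so changing the structure alters neither N nor the stated power.

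**Visit-specific intervals, complete data.** Residual variance at visit t is v_t = SD_t² × (1 − r_t²), where r_t is the correlation of baseline with that visit. Compound symmetry replaces each v_t by the mean v̄. Hence
- model SE / true SE = √(v̄ / v_t) = k_t
- coverage of a nominal 95% interval = 2Φ(1.96 k_t) − 1

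The SDs and correlations below are assumptions, except that SD 2 is the plan's single value.

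| Assumed SD (10 wk / 6 mo / 12 mo) | Assumed r_t | v_t | k_t | 10-week coverage | 12-month coverage |
|---|---|---|---|---|---|
| 2 / 2 / 2 | .60 / .60 / .60 | 2.56 / 2.56 / 2.56 | 1.00 / 1.00 / 1.00 | 95.0% | 95.0% |
| 2 / 2 / 2 | .60 / .57 / .55 | 2.56 / 2.70 / 2.79 | 1.02 / 1.00 / 0.98 | 95.5% | 94.5% |
| 2 / 2 / 2 | .65 / .55 / .50 | 2.31 / 2.79 / 3.00 | 1.08 / 0.98 / 0.95 | 96.6% | 93.7% |
| 1.9 / 2.1 / 2.3 | .65 / .55 / .50 | 2.08 / 3.08 / 3.97 | 1.21 / 0.99 / 0.88 | 98.2% | 91.4% |

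Worked example, third row: v̄ = (2.31 + 2.79 + 3.00)/3 = 2.70 and k at 12 months = √(2.70/3.00) = 0.949. Then 1.96 × 0.949 = 1.86, which gives 93.7%.

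The first and third rows share the plan's SD of 2. A constant raw SD does not by itself remove the problem; constant variance after baseline adjustment does. If adjusted variance fell over time, the pattern would reverse.

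**Primary contrast, complete data.** The variance of a person's mean residual over three visits is (mean variance + 2 × mean covariance)/3. Compound symmetry estimates both means without bias, so the averaged contrast keeps the right standard error. In simulation (250 per arm, baseline-adjusted SD 1.4/1.6/1.8) the model SE was 0.123 under both structures.

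**With dropout.** Simulations used 250 per arm, 500 repetitions, baseline-adjusted SD 1.4/1.6/1.8, about 17% missing at 12 months, and missing-at-random dropout running in opposite directions by arm. Ranges are over two assumed correlation patterns.

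| Quantity | Random intercept | Unstructured |
|---|---|---|
| 12-month 95% coverage | about 0.88 | 0.93-0.94 |
| 10-week 95% coverage | 0.98-0.99 | 0.94-0.96 |
| 12-month bias, BPI points | 0.03-0.05 | at most 0.01 |
| Averaged-contrast bias, BPI points | about 0.02-0.03 | at most 0.01 |
| Averaged-contrast 95% coverage | 0.94-0.95 | 0.93-0.97 |

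Monte Carlo error on coverage is √(0.95 × 0.05/500) ≈ 1 point, and about 1.5 points near 0.88. With equal residual SDs but unequal correlations, the limiting 12-month bias under the same type of dropout was about 0.04 with a random intercept and near zero unstructured. With equal SDs and equal correlations, the random-intercept model was unbiased.

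**The case against.** The plan does not say compound symmetry. A model described as one that "will be fitted in a mixed model for repeated measures as a function of the group assignment" can equally be fitted with an unstructured residual matrix, and the text does not exclude one. That stands: the structure is implied by the wording, not fixed by it. But the participant effect is the only within-person term written, the text goes on to call these linear mixed effect models, and adding a random intercept to a fully unstructured matrix is redundant. The literal reading is therefore the random-intercept one. The alternative reading leaves the choice open until data are seen.

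A reader might infer that type I error is inflated, since at alpha 0.0167 the 12-month contrast would reject at 0.023 or 0.036 in the last two scenarios of the first table. The documents do not support that. The alpha statement, "This is based on an alpha level of 0.0167 (Bonferroni correction of 0.05/3 = 0.0167) for each of the three comparisons", concerns pairwise arm comparisons, and the visit-level differences are to be estimated, with no test at that level assigned to them. Interval coverage is the relevant measure.

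A reader might also infer that the 12-month interval is certainly too narrow. That needs variance to rise over time, and nothing in the documents shows it.

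On dropout, the planned selection models already use observed outcome values under several missingness mechanisms, and the bias is small. Both points stand. Those analyses address missingness, however, and do not repair the visit-specific standard errors in the initial analysis.

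**Conclusion.** The point holds for the visit-specific estimates and the continuous secondary outcomes, conditional on residual variance differing by visit. Under plausible but assumed inputs, the loss of 12-month coverage runs from negligible (94.5%) to about 3.6 points (91.4%) with complete data, and to about 88% with dropout and steeply rising variance. It is zero with complete data if adjusted variance is constant.

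It would be wrong to conclude that the primary test is invalid. The whole-follow-up contrast is essentially unaffected with complete data. Under dropout the added bias of about 0.02-0.03 points is 2-3% of the 1-point important difference, and at most 0.03/0.66 ≈ 5% of the detectable difference (0.33 × 2 = 0.66). Even 0.05 at 12 months is small on that scale.

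The visit SDs, correlations and dropout mechanism are assumptions; the documents supply only the single SD of about 2. This is a worthwhile improvement to the plan that leaves its main conclusion intact.

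**What to change.** In section 5.6, General Analytic Approach:
- Replace the random-effect clause with an unstructured within-participant covariance over the three follow-up visits, fitted by REML, and name a fallback for non-convergence only (for example heterogeneous Toeplitz).
- Add the group-by-time term. Visit-specific differences need it, and the model as written does not list it.
- Keep the whole-follow-up difference as the primary test, defined as the equally weighted average of the three visit differences. The definition matters because, under an unstructured covariance without the interaction, the group coefficient would no longer weight the visits equally.
- Apply the same specification to the continuous secondary outcomes.
- A baseline slope that varies by visit is optional.

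The cost is a sentence or two. Three visits need six covariance parameters (3 × 4/2), against at least 3 × 250 = 750 participants. Sample size, alpha, the primary comparison and data collection do not change.
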